13.3.4.8 Mitral Regurgitation

Color flow Doppler imaging of the left atrium should be performed from the parasternal long-axis view, and from the apical 4, 2, and long axis views.

Mitral regurgitant (MR) jets should be recorded with CW Doppler using a velocity scale that allows assessment of the density, shape, duration, and peak velocity of the MR jet. If severity appears moderate or greater by visual assessment, pulmonary vein velocities should be recorded with PW Doppler to assess for the presence of systolic flow reversal. A spectral Doppler recording of mitral inflow should be recorded to assess the early filling velocity (E) and the A wave inflow pattern. If image quality is technically adequate, quantitative assessment of the mitral regurgitant orifice area using PISA, or derivation of regurgitant volume and regurgitant fraction (stroke volume method) can be performed. Grading of the severity of mitral regurgitation should be integrative using the parameters in Table 18.⁸³

Table 18. Parameters for grading the severity of mitral regurgitation

Parameter	Mild	Moderate	Severe
Structural			
MV Morphology	None or mild leaflet abnormality (e.g., mild thickening, calcifications or prolapse, mild tenting)	Moderate leaflet abnormality or moderate tenting	Severe valve lesions (primary: flail leaflet, ruptured papillary muscle, severe retraction, large perforation; secondary: severe tenting, poor leaflet coaptation)
LA and LV Size [†]	Usually normal	Normal or mildly dilated	Dilated [†]
Qualitative Doppler			
Color flow jet areas [§]	Small, central, narrow, often	Variable	Large central jet (>50% of LA) or eccentric wall-impinging jet of variable size
Flow convergence [‡]	Not visible, transient or small	Intermediate in size and duration	Large throughout systole
CWD jet	Faint/partial/parabolic	Dense but partial or parabolic	Holosystolic/dense/triangular
Semi-quantitative			
Vena contracta width (cm)	<0.3	Intermediate	≥0.7 (>0.8 for biplane)
Pulmonary vein flow	Systolic dominance (may be blunted in LV dysfunction or AF)	Normal or systolic blunting	Minimal to no systolic flow systolic flow reversal
Mitral inflow	A-wave dominant	Variable	E-wave dominant (>1.2 m/sec)
Quantitative			
EROA, 2D PISA (cm ²)	<0.20	0.20-0.39	≥0.40 (may be lower in secondary MR with elliptical ROA)
RVol (mL)	< 30	30-44	≥ 60
RF (%)	< 30	30-49	≥ 50

EROA, Effective regurgitant orifice area; RVol, Regurgitant volume; RF, Regurgitant fraction; PISA, Proximal isovelocity surface area
 Bolded qualitative and semiquantitative signs are considered specific for their MR grade.

[†]This pertains mostly to patients with primary MR.

[‡]LV and LA can be within the “normal” range for patients with acute severe MR or with chronic severe MR who have small body size, particularly women, or with small LV size preceding the occurrence of MR.

[§]With Nyquist limit 50-70 cm/sec.

^K Small flow convergence is usually <0.3 cm, and large is ≥ 1 cm at a Nyquist limit of 30-40 cm/sec.

13.3.4.9 Tricuspid Regurgitation and Estimated RVSP

Color flow imaging of the right atrium should be performed from the apical 4-chamber view, the parasternal long-axis view of the RVOT, and the parasternal short-axis view at the level of the aortic valve.

Tricuspid regurgitant (TR) jets should be recorded with CW Doppler using a velocity scale that allows assessment of the density, shape, duration, and peak velocity of the TR jet. If severity appears mild or greater by visual assessment, hepatic vein and tricuspid inflow velocities should be recorded with PW Doppler to assess systolic flow reversal and tricuspid inflow pattern, respectively. If image quality is technically adequate, quantitative assessment of the regurgitant orifice area using PISA, or derivation of regurgitant volume (stroke volume method) can be performed. Grading of the severity of tricuspid regurgitation should be integrative using the parameters in Table 19.⁸³

Table 19. Parameters for grading the severity of tricuspid regurgitation

Parameter	Mild	Moderate	Severe
Structural			
TV Morphology	Normal or mildly abnormal leaflets	Moderately abnormal leaflets	Severe valve lesions (e.g., flail leaflet, severe retraction, large perforation)
RV and RA Size ⁺	Usually normal	Normal or mildly dilated	Usually dilated ⁺
Qualitative Doppler			
Color flow jet area	Small, narrow, central	Moderate central	Large central jet or eccentric wall-impinging jet of variable size
Flow convergence	Not visible, transient or small	Intermediate in size and duration	Large throughout systole
CWD jet	Faint/partial /parabolic	Dense, parabolic or triangular	Dense, often triangular
Semi-quantitative			
Color flow jet area (cm ²) [†]	Not defined	Not defined	> 10
Vena contracta width (cm)	<0.3	0.3-0.69	≥ 0.7
PISA radius (cm) [‡]	≤0.5	0.6-0.9	> 0.9
Hepatic vein flow [§]	Systolic dominance	Systolic blunting	Systolic flow reversal
Tricuspid inflow [§]	A-wave dominant	Variable	E-wave >1.0 m/sec
Quantitative			
EROA, 2D PISA (cm ²)	<0.20	0.20-0.39	≥ 0.40
RVol (mL)	<30	30-44	≥ 45

RA, Right atrium; RV, Right ventricle; EROA, Effective regurgitant orifice area; RVol, Regurgitant volume; PISA, Proximal isovelocity surface area
 Bolded signs are considered specific for their TR grade.

*RV and RA size can be within the “normal” range in patients with acute severe TR

[†]With Nyquist limit >50-70 cm/sec.

[‡]With baseline Nyquist limit shift of 28 cm/sec.

[§]Signs are nonspecific and are influenced by many other factors (RV diastolic function, atrial fibrillation, RA pressure).

13.3.4.10 Right Ventricular Function

The right ventricle (RV) should be imaged from the apical four-chamber, RV-focused apical 4-chamber, left parasternal long- and short-axis, left parasternal RV inflow, and subcostal views. In most cases, visualization of the entire RV free wall is better in the RV-focused view (transducer angled medially) than the standard 4-chamber view. Therefore, the RV-focused view is recommended for measurements.⁸⁰ The following measurements should be obtained to evaluate RV function (Figure 20):

- Basal RV internal dimension at end-diastole
- RV internal area at end-diastole
- RV internal area at end-systole
- Tricuspid annular plane systolic excursion (TAPSE)

[figure not shown]

Figure 20. (A) Measurement of basal RV linear dimension; maximal transversal dimension in the basal 1/3 of RV inflow at end-diastole (RV-focused view); (B) TAPSE by m-mode, measured between end-diastole and peak systole. Proper alignment of m-mode cursor with the direction of RV longitudinal excursion should be achieved from the apical approach; (C) Example of measurement of RV areas: manual tracing of RV endocardial border from the lateral tricuspid annulus along the free wall to the apex and back to medial tricuspid annulus, along the interventricular septum at end-diastole and at end-systole. Trabeculations, papillary muscles and moderator band are included in the cavity area. [Journal of the American Society of Echocardiography 2015 281-39.e14DOI: (10.1016/j.echo.2014.10.003) Copyright © 2015 American Society of Echocardiography]

13.3.5 Echocardiography Core Lab Analysis

Protocol-required and endpoint or event related (as applicable) echocardiograms will be sent to the ECL for assessment: the data generated by the ECL will be the primary data used for analysis and reporting. Received echocardiograms will be logged in and analyzed by the ECL according to their procedures determined for this study. Qualitative assessment of valvular regurgitation and quantitative analysis of variables related to hemodynamic valve performance, cardiac function and cardiac dimensions will be performed according to the methods described in Section 13.3.2.

The ECL will report the following variables:

- Height (cm) and weight (kg)
- Heart rate (HR)
- Left ventricular outflow tract (LVOT) diameter in mid systole
- Max aortic or prosthetic valve velocity (vMax) by CW Doppler
- Aortic or prosthetic valve velocity time integral (VTI) by CW Doppler
- Mean gradient across aortic or prosthetic aortic valve (MG) by CW Doppler
- LVOT VTI by PW Doppler
- Systolic ejection time (ET)
- Grade of native aortic regurgitation (baseline only)
- Grade of prosthetic paravalvular regurgitation (post-implant only)
- Grade of prosthetic transvalvular regurgitation (post-implant only)
- Right ventricular outflow tract (RVOT) diameter (post-implant; if AR > mild by visual estimate)
- RVOT VTI (post-implant; if aortic regurgitation > mild by visual estimate)
- Grade of prosthetic total (transvalvular plus paravalvular) regurgitation (post-implant only)
- Grade of mitral regurgitation (MR)
- Grade of tricuspid regurgitation (TR)
- Max TR jet velocity (if TR is present)
- Left ventricular internal dimension at end diastole (LVIDD)
- Left ventricular internal dimension at end systole (LVIDS)
- Interventricular septal thickness at end diastole (IVS)
- Left ventricular posterior wall thickness at end diastole (LVPW)
- Left ventricular end diastolic volume by modified Simpson's rule (LVEDV)
- Left ventricular end systolic volume by modified Simpson's rule (LVESV)
- Left atrial volume at end systole by bi-plane Simpson's rule (LAV)
- Left atrial internal linear dimension at end systole (LA)
- Mitral inflow early (E) velocity
- Mitral inflow atrial (A) velocity
- Mitral inflow E wave deceleration time (MdT)
- Mitral annular early (e') diastolic velocity; lateral
- Mitral annular late (a') diastolic velocity; lateral
- Mitral annular early (e') diastolic velocity; medial

- Mitral annular late (a') diastolic velocity; medial
- Grade of diastolic dysfunction
- Pattern of LV geometry
- Peak average left ventricular global longitudinal strain (GLS) measured at end systole (aortic valve closure)
- Vendor, model, and software version of echocardiography system
- Tricuspid annular plane systolic excursion (TAPSE)
- Basal right ventricular linear dimension at end diastole (RVD)
- Right ventricular area at end diastole (RVAD)
- Right ventricular area at end systole (RVAS)

In addition, the following variables will be derived by the central database from the appropriate measurements reported by both the site and ECL.

- **Body Surface Area (BSA) in m²**
BSA = $0.007184 \times \text{height} \times \text{weight} \times 0.425$
Where: BSA is the body surface area in cm², height is in cm, and weight is in kg⁸
- **Body Mass Index (BMI) in kg/cm**
BMI = weight in kg/height in cm
- **Aortic Valve Area (AVA) in cm²**
AVA = LVOT diameter in cm² x 0.785 x (LVOT VTI/aortic valve VTI)
Where: LVOT VTI is the velocity time integral of the left ventricular outflow tract in cm, and aortic valve VTI is the velocity time integral of the native aortic valve in cm
- **Aortic Valve Area Index (AVAI) in cm²/m²**
AVAI = AVA/BSA
Where: AVA is the native aortic valve area in cm², and BSA is the body surface area in m²
- **Effective Orifice Area (EOA) in cm²**
EOA = LVOT diameter² x 0.785 x (LVOT VTI/Aortic valve VTI)
Where: LVOT VTI is the velocity time integral of the left ventricular outflow tract in cm, and aortic valve VTI is the velocity time integral of the aortic prosthesis in cm
- **Effective Orifice Area Index (EOAI) in cm²/m²**
EOAI = EOA/BSA
Where: EOA is the effective orifice area in cm², and BSA is the body surface area in m²
- **Doppler Velocity Index (DVI)**
DVI = LVOT VTI/Aortic valve VTI
Where: LVOT VTI is the velocity time integral of the left ventricular outflow tract in cm, and aortic valve VTI is the time velocity integral of the prosthetic aortic valve in cm

⁸ Height will be pulled from the site baseline eCRF, and weight will be pulled from the site eCRF for the visit

- **Estimated Right Ventricular Systolic Pressure (RVSP) in mmHg**
 $RVSP = (4 \times MVTR \text{ jet}^2) + 10$
Where: MV TR jet is the max velocity of the tricuspid regurgitant jet, and 10 = the assumed mean right atrial pressure in mmHg
- **Cardiac Output (CO) in l/min**
 $CO = (SV \times HR)/1000$
Where: SV is the stroke volume in ml/beat, and HR is the heart rate in beats per minute
- **Cardiac Index (CI) in l/min/m²**
 $CI = CO/BSA$
Where CO is the cardiac output in l/min and BSA is Body Surface Area in cm²
- **Stroke Volume (SV) in ml/beat**
 $SV = LVOT \text{ diameter}^2 \times 0.785 \times LVOT \text{ VTI}$
Where: LVOT VTI is the velocity time integral from the left ventricular outflow tract in cm
- **Stroke Volume Index (SVI) in ml/beat/m²**
 $SVI = SV/BSA$
Where SV is stroke volume in ml/beat and BSA is Body Surface Area in m²
- **Stroke Volume RVOT (SV RVOT) in ml/beat**
 $SV \text{ RVOT} = RVOT \text{ diameter} \times RVOT \text{ VTI}$
Where RVOT diameter is the right ventricular outflow tract diameter in cm and RVOT VTI is the right ventricular velocity time integral
- **Aortic Regurgitant Volume (ARVol) in ml/beat**
 $RV = SV - SV \text{ RVOT}$
Where: $SV = LVOT \text{ diameter}^2 \times 0.785 \times LVOT \text{ VTI}$, and $SV \text{ RVOT} = RVOT \text{ diameter}^2 \times 0.785 \times RVOT \text{ VTI}$
- **Aortic Regurgitant Fraction (ARF) in %**
 $ARF = ARVol/SV$
Where ARVol is the aortic regurgitant volume in ml and SV is the stroke volume in ml
- **Left Atrial Volume Index (LAVI)**
 $LAVI = LAV/BSA$,
Where LAV is left atrial volume (biplane Simpson's) at end systole in ml, and BSA is body surface area in m²
- **Aortic transvalvular flow rate (AFR) in ml/second**
 $AFR = SV/ET$
Where SV is the stroke volume in ml/beat and ET is systolic ejection time in milliseconds
- **Valvulo-arterial impedance (Z_{va})**
 $Z_{va} = (MG + SAP)/SVI$
Where MG is mean aortic gradient in mmHg, SAP is systolic blood pressure in mmHg⁹, and SVI is stroke volume index in ml/beat/m² body surface area

⁹ Systolic blood pressure will be pulled from the site eCRF

- **E:e'**
Mitral inflow early (E) velocity/(mitral annular early (e') diastolic velocity; lateral + mitral annular early (e') diastolic velocity; medial)/2
- **E:A Ratio**
Mitral inflow early (E) velocity/ mitral inflow atrial (A) velocity
- **Left ventricular ejection fraction (LVEF) by modified-Simpson's rule**
$$\text{LVEF} = \frac{\text{LVEDV} - \text{LVESV}}{\text{LVEDV}} \times 100$$

Where LVEDV is left ventricular end-diastolic volume in ml and LVESV is left ventricular end systolic volume
- **Fractional Shortening (FS) in %**
$$\text{FS} = \frac{\text{LVIDD} - \text{LVIDS}}{\text{LVIDD}} \times 100$$

Where: LVIDD is left ventricular internal dimension at end diastole in cm, and LVIDS is left ventricular internal dimension at end systole in cm
- **Relative wall thickness (RWT)**
$$\text{RWT} = \frac{\text{IVS} + \text{LVPW}}{\text{LVIDD}}$$

Where IVS is interventricular septal thickness at end-diastole in cm, LVPW is left ventricular posterior wall thickness at end-diastole in cm, and LVIDD is left ventricular internal dimension at end-diastole in cm
- **Left Ventricular Mass (LVM) in grams**
$$\text{LVM} = 0.83 \times [(\text{LVIDD} + \text{LVPW} + \text{IVS})^3 - (\text{LVIDD})^3] + 0.6$$

Where: LVIDD is the left ventricular internal dimension at end diastole in cm, LVPW is the left ventricular posterior wall thickness at end diastole in cm, and IVS is the interventricular wall thickness at end diastole in cm.
- **Left Ventricular Mass Index (LVMI) in g/m² body surface area**
$$\text{LVMI} = \text{LVM} / \text{BSA}$$

Where: LVM is left ventricular mass in g, and BSA is body surface area in m²
- **Right Ventricular Fractional Area Change (RVFAC) in %**
$$\text{RVFAC} = \frac{\text{RVAD} - \text{RVAS}}{\text{RVAD}} \times 100$$

Where RVAD is right ventricular area at end diastole and RVAS is right ventricular area at end-systole

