 - Invasive diagnostic evidence with right heart catheterization showing a pulmonary capillary wedge pressure (pulmonary artery occlusion pressure) \geq 18 mmHg, central venous pressure \geq 12 mmHg, or a cardiac index < 2.2 L/min/m²
- 4) The patient receives at least one of the following treatments specifically for HF:
 - Initiation of intravenous diuretic or vasoactive agent (e.g. inotrope, vasopressor, or vasodilator)
Note that signification augmentation of oral diuretic therapy will not be sufficient to fulfill the urgent HF visit criteria
 - Mechanical or surgical intervention, including:
 - Mechanical circulatory support (e.g. intra-aortic balloon pump, ventricular assist device, extracorporeal membrane oxygenation, total artificial heart)
 - Mechanical fluid removal (e.g. ultrafiltration, hemofiltration, dialysis)

*Note that clinic visits for scheduled administration of HF therapies or procedures (e.g. intravenous diuretics, intravenous vasoactive agents, or mechanical fluid removal) **do not** qualify as non-hospitalized HF events.*

Device Success⁶³

All of the following:

- Absence of procedural mortality, **AND**
- Correct positioning of a single prosthetic heart valve into the proper anatomical location, **AND**
- Absence of patient prosthesis-mismatch and mean aortic valve gradient < 20 mmHg (or peak velocity < 3 m/sec), **AND**
- Absence of moderate or severe prosthetic valve regurgitation.

Bioprosthetic Valve Dysfunction (BVD)⁶³: Any of the following

- **Stenosis: moderate/severe**; any of the following:
 - Peak aortic velocity > 4 m/s OR mean aortic gradient > 40 mmHg, AND EOA < 0.8 cm²
 - Peak aortic velocity > 4 m/s OR mean aortic gradient > 40 mmHg, AND EOA ≥ 0.8 cm², **AND** DVI < 0.25
 - Peak aortic velocity ≤ 4 m/s and mean aortic gradient ≤ 40 mmHg, AND EOA < 0.8 cm², **AND** DVI < 0.25
- **Paravalvular regurgitation: moderate**
- **Paravalvular regurgitation: severe**
- **Transvalvular regurgitation: moderate**
- **Transvalvular regurgitation: severe**
- **Total regurgitation: moderate**
- **Total regurgitation: severe**

Notes:

1. For subjects with BSA < 1.6 m², the EOA criteria for significant (moderate or severe) stenosis is < 0.6 cm²
2. For subjects with LVOT diameter > 2.5 cm, the DVI criteria for significant (moderate or severe) stenosis is < 0.2
3. Reporting of prosthetic valve dysfunction will be based on core lab results.

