7.9.2.3 Heart failure events at 30 days and 6 months

Heart failure events will be adjudicated by the CEC and analysis will be based on data collected on the CEC adjudication form. The endpoint will be analyzed with Kaplan-Meier survival analysis according to Section 7.2 for each time point. The primary analysis will use the Attempted Implant set.

7.9.2.4 Hemodynamic performance metrics by Doppler echocardiography at discharge, 30 days, and 6 months

The following hemodynamic performance metrics by Doppler echocardiography will be reported at discharge, 30 days, and 6 months:

- Mean aortic gradient
- Effective orifice area
- Degree of total, para, and transvalvular prosthetic regurgitation
- Incidence of moderate and severe patient-prosthesis mismatch (PPM)

Endpoint Definitions:

Mean aortic gradient will be reported in units of mmHg.

Effective Orifice Area (EOA) in cm² will be derived according to the following formula

$$EOA = LVOT\ diameter^2 \times 0.785 \times (LVOT\ VTI / Aortic\ valve\ VTI)$$

Where: LVOT VTI is the velocity time integral of the left ventricular outflow tract in cm, and aortic valve VTI is the velocity time integral of the aortic prosthesis in cm.

Degree of total, para, and transvalvular prosthetic regurgitation will be reported in categories of none, trace, mild, moderate, and severe.

Patient-prosthesis mismatch (PPM)⁽¹⁾ is defined as follows:

For subjects with body mass index (BMI) < 30 kg/cm²

- **Moderate PPM:** EOAI = 0.85 – 0.65
- **Severe PPM:** EOAI < 0.65

For subjects with BMI ≥ 30 kg/cm²

- **Moderate PPM:** EOAI = 0.70 – 0.60
- **Severe PPM:** EOAI < 0.60.

Note that in the above, Effective Orifice Area Index (EOAI) in cm²/m² is defined as EOAI = EOA/BSA where EOA is the effective orifice area in cm² and BSA is the body surface area in m².

Analysis Methods:

Data for all endpoints will be reported on the core lab echo CRF. Mean aortic gradient and EOA will be summarized descriptively as continuous outcomes at each time point. Change from baseline in mean aortic gradient and EOA will also be summarized descriptively along with two-sided 95% confidence interval and p-value from a paired t-test. The degree of total, para, and transvalvular prosthetic regurgitation and incidence of moderate and severe PPM will be summarized with frequency counts and percentages at each follow-up time point. Analysis of each hemodynamic performance outcome will use the Implanted set.

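### Three derived-variable formulas in CIP 13.3.5 are wrong or contradictory as printed: BSA (subject to a check of the source file), RVOT stroke volume and transvalvular flow rate

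*Protocol*

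**What the plan says.** CIP 13.3.5 (Echocardiography Core Lab Analysis) assigns a set of variables to the central database, to be computed from site and core-lab measurements. Three entries matter here.

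- **BSA.** The heading is "Body Surface Area (BSA) in m²". The formula is printed as 0.007184 × height × weight × 0.425, and the definition beneath it says "BSA is the body surface area in cm², height is in cm, and weight is in kg". The Cardiac Index entry repeats the second unit: "CO is the cardiac output in l/min and BSA is Body Surface Area in cm²". The entries for AVAI, EOAI, SVI, LAVI and LVMI all take BSA in m². So does SAP 7.9.2.4 ("EOA is the effective orifice area in cm² and BSA is the body surface area in m²"), which gives no BSA formula of its own.
- **RVOT stroke volume.** Its own entry is diameter × VTI, explained as "Where RVOT diameter is the right ventricular outflow tract diameter in cm and RVOT VTI is the right ventricular velocity time integral". The next entry, aortic regurgitant volume, defines the same quantity as diameter² × 0.785 × VTI.
- **Aortic transvalvular flow rate (AFR).** The heading is ml/second and the formula is SV/ET: "Where SV is the stroke volume in ml/beat and ET is systolic ejection time in milliseconds".

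The plan also shows what scale it expects for BSA. The note on bioprosthetic valve dysfunction in CIP 13.8.3 reads "For subjects with BSA < 1.6 m², the EOA criteria".

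**The concern.** The list reads as a programming specification, and nothing in the SAP overrides it. BSA is the denominator of EOAI, which decides PPM and through it device success (SAP 7.9.2.1 and 7.9.2.4). It is also the denominator of SVI, a named efficacy endpoint. SAP 7.9.2.11 refers SVI to the core-lab form, but SVI is not among the variables that CIP 13.3.5 says the core lab reports, so it has to come from the derivation. BSA also enters AVAI, LAVI, LVMI and cardiac index, and it triggers the small-body rule for valve dysfunction.

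The two RVOT definitions are a quieter hazard. Both give values that look like stroke volumes, so a wrong choice might go unnoticed. The flow-rate entry is a plain unit error.

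**Working it through.** The documents give no worked value for any of these variables, so there is no stated figure to reproduce. The check evaluates each formula as printed and compares it with the plan's own units, cut-offs and duplicate definitions. Body sizes and echo values are illustrative assumptions.

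**1. BSA.** As printed, BSA = 0.007184 × 0.425 × height × weight = 0.003053 × height × weight. The comparison column puts 0.425 as an exponent on weight and 0.725 on height. The documents give no height exponent, so 0.725 is an assumption.

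| Height/weight | BSA as printed | BSA with both exponents | Ratio | EOAI at EOA 2.5 cm²: printed / exponents | SVI at SV 75 ml: printed / exponents |
|---|---|---|---|---|---|
| 150 cm/50 kg | 22.9 | 1.43 | 16.0 | 0.109 / 1.75 | 3.3 / 52.4 |
| 160 cm/65 kg | 31.8 | 1.68 | 18.9 | 0.079 / 1.49 | 2.4 / 44.7 |
| 170 cm/80 kg | 41.5 | 1.92 | 21.7 | 0.060 / 1.31 | 1.8 / 39.2 |
| 180 cm/95 kg | 52.2 | 2.15 | 24.3 | 0.048 / 1.16 | 1.4 / 34.9 |
| 190 cm/120 kg | 69.6 | 2.47 | 28.2 | 0.036 / 1.01 | 1.1 / 30.4 |

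- *Against the plan's own scale.* To reach 1.6, height × weight would have to be 1.6/0.003053 = 524, or 3.3 kg at 160 cm. The cm² label does not rescue the formula, since 1.6 m² is 16,000 cm².
- *Partial restoration.* With an exponent on weight only, the range is 5.7 to 10.4, still far from 1.6.
- *Sensitivity to the assumed exponent.* At 170 cm/80 kg, height exponents from about 0.66 to 0.78 give roughly 1.4 to 2.5 m². The scale agrees with the plan, but 0.725 itself is not established by it.
- *PPM and device success.* The lower severe-PPM limit over the two BMI branches is EOAI 0.60. At the smallest body size above, escaping it needs EOA ≥ 0.60 × 22.9 = 13.7 cm². The whole area of the largest annulus that the device covers (30 mm, CIP 9.2) is 0.785 × 3.0² = 7.1 cm². Every subject in this range would be severe, and device success would be 0%.
- *AVAI.* An AVA of 1.2 cm² gives 0.052 down to 0.017, so the 0.6 limit is always met.

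**2. RVOT stroke volume.** Assume RVOT diameter 2.5 cm, RVOT VTI 14 cm, LVOT diameter 2.2 cm and LVOT VTI 25 cm.

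- Own entry: 2.5 × 14 = 35.0, in cm², which is not a volume.
- Regurgitant-volume entry: 2.5² × 0.785 × 14 = 68.7 ml.
- LVOT stroke volume: 2.2² × 0.785 × 25 = 95.0 ml.
- Regurgitant volume: 95.0 − 68.7 = 26.3 ml (28%) by the formula in its own entry, against 95.0 − 35.0 = 60.0 ml (63%) if the shorter line were reused. By fraction, CIP Table 17 reads these as mild and severe.

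A lost superscript does not explain the shorter line, because the factor 0.785 is missing too.

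**3. Flow rate.** With SV 70 ml and ET 320 ms, the printed formula gives 70/320 = 0.219. In ml/second it is 70/0.320 = 219, a factor of 1000.

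**The case against.** The strongest objection concerns BSA. The text was read from a PDF, and 0.425 looks like a displaced exponent. Squares and cubes elsewhere in the section survived, but the section offers no other decimal exponent for comparison, so that shows little. If the source file carries both exponents, every BSA figure above falls away and only the cm² labels remain. This stands, and the BSA consequence has to be stated as conditional.

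Second, a reader might infer that regurgitant volume and fraction will be wrong. The documents do not support that. The regurgitant-volume entry carries the complete RVOT formula, and followed as written it is sound. Regurgitation is also graded by the core lab from several parameters together, and RVOT data are collected only when regurgitation looks more than mild, so regurgitant volume is one supporting input.

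Third, a reader might infer that eligibility is compromised. The effect is limited. AVAI ≤ 0.6 cm²/m² is an alternative to AVA ≤ 1.0 cm², a gradient or velocity criterion must also be met (CIP 6.2.1), and the core lab and the Eligibility Review Committee confirm severity.

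Fourth, controls exist. CIP 12.3.2 plans a validated database with range and logic checks, and SAP section 8 requires independent validation of the analysis datasets and the endpoints. A BSA near 40 would probably be noticed. But the checks in 12.3.2 are described for entered data, and SAP section 8 does not say that the formulas themselves are tested. A programmer who validates faithfully against 13.3.5 would reproduce its errors. The controls reduce the risk without removing the defect.

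**Conclusion.** The specification needs correcting, with different certainty for each part.

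- **Certain from the text:** BSA is labelled cm² in two places against m² everywhere else; RVOT stroke volume has two incompatible definitions, and the stand-alone one is dimensionally wrong; AFR is off by 1000 against its own heading. AFR is not an endpoint or outcome measure in either document.
- **Conditional:** the BSA formula is unusable as printed. If the source document and the database follow the printed product, PPM is severe for everyone, device success is 0% and SVI is 16 to 28 times too small. The size of the SVI error rests on the assumed height exponent; the PPM and device-success result does not.
- **Not supported:** that BSA-indexed results or regurgitant volumes will in fact be wrong. That would require literal programming of the BSA product, or reuse of the shorter RVOT line, and the documents show neither.

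The study is descriptive, so no power or error rate is affected. The point still matters because SVI, PPM and device success are efficacy endpoints that depend on BSA.

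**What to change.** 1. Check the BSA entry in the source document and in the database specification. If both exponents are there, only the cm² labels need changing.
2. Otherwise, state one BSA formula in m² in CIP 13.3.5, with explicit exponents on height and weight, and repeat it in SAP 7.9.2.4. The form 0.007184 × height(cm)^0.725 × weight(kg)^0.425 fits the plan's scale, but the sponsor must confirm 0.725 against its own source.
3. Change cm² to m² in the BSA and Cardiac Index definitions.
4. Write RVOT stroke volume as RVOT diameter² × 0.785 × RVOT VTI in both entries.
5. Write AFR = SV/(ET in ms/1000).
6. Before the first analysis, verify the programmed derivations against the corrected list, with a few hand-calculated subjects.

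The cost is a wording correction in the CIP and SAP plus a check of the derivation code. No new data or visits are needed.
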